The presence of diarrhoea is generally assessed by questionnaire, asking whether a child has experienced three or more loose or liquid stools in a given period, typically in the past 24 hours or two weeks. However, despite the importance of this, there are few studies on the validity of this tool - with the few studies that have been conducted suggesting that current methods are not performing well (Schmidt et al, 2011). Longer recall periods, such as two weeks, are subject to fallible memory and recall bias. Shorter periods are additionally affected by other biases. For example, the more frequently a person is asked about diarrhoea, the less likely they are to report diarrhoea (Clasen et al, 2014). It has also been found that diarrhoea rates are subject to Hawthorne effects, differential behaviour due to knowledge of being observed (Leonard et al, 2006). Additionally, while loose and liquid stool are generally defined by taking the shape a container, judgement on the specifics of this may also vary between individuals. These biases may be reduced by a more comprehensive survey including pictures, such as the Bristol Stool Chart (Lewis et al, 1997). Likewise, stunting, the other outcome often used in studies of WASH interventions, is a commonly used outcome measure in studies of gastrointestinal health, however the multiple causes of growth retardation and time required for it to manifest mean it is unlikely to be sensitive to intervention in anything but the longest duration studies.

Aims and Objectives

Despite the importance of the topic there have been few studies on the accuracy and reliability of diarrhoea measurement methods. The aim of this study it to evaluate the accuracy of reported diarrhoea rates as a proxy for enteric infection, using both a standard and enhanced reporting method for diarrhoea, with sub-aims:

- To assess the relative differences between "standard" and "enhanced" questionnaires.
- To analyse the pathogenic profile of stool samples.
- Determining carriage of pathogens from Myanmar to Bangladesh.

Design and Methodology

Sampling

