The study will follow a two arm RCT design in which 400 households will be recruited through random household sampling in both the formal and informal refugee camps in Cox's Bazar (Fig.1). The random household sampling will use an EPI sampling method, in which a series of random angles and distances from a pre-determined central point (e.g. a water tap) will be generated, selecting households closest to the mapped location. This list will be generated at the beginning of the data collection period, with households randomly assigned to each research assistant.

Inclusion and exclusion criteria

Inclusion and exclusion criteria for the study is as follows:

Inclusion	Exclusion
Household has at least one child under the age of five	Household is expecting to relocate/resettle/repatriate in the next 6 months
Household has at least one adult over the age of 18	
Household consents to study	

Recruitment

Households will be initially contacted by research assistants travelling door to door who will ask to speak with an adult in the household. The study will be explained through the use of the participant information sheet, with households meeting inclusion criteria being consented and enrolled in the study. As part of consenting, GPS coordinates, name, and mobile phone number will be recorded. Households who do not consent will not have mobile phone numbers recorded, but will have GPS coordinates recorded to ensure that the house is not approached again. Mobile phone numbers and GPS coordinates will be recorded separately from data in a log book, and linked to individual household identifiers which will be recorded on the survey form.

Diarrhoea survey

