Households will be randomised in a 1:1 ratio into the basic survey, a survey asking if a child had diarrhoea and dysentery in the past two weeks, based on DHS survey measures; and the enhanced survey, based on qualified stool charts (of which images will be displayed on the tablet during surveying), proxies for diarrhoea (such as oral intake), and measures of waterwashed diseases. All households will also be administered a basic demographic survey with questions on education, health, living environment, and WASH usage. If a household reports dysentery, they will be given the information of a local clinic for treatment. All surveys will be translated into Rohingya, and back translated into English – with translation following WHO guidelines: aiming for the simplest translation with the conceptual equivalent, targeted toward the target audience or Rohingya refugees, many of whom are illiterate with a low level of education. This will be done through consultation with Rohingya community members to ensure proper translation.

Data collection will take place at two time points: February/March and June/July. Research assistants will collect data through the use of ODK on an Android tablet. Data will be stored on the tablets and uploaded to Warwick servers at the end of each day, when research assistants return to the base office. Data will be additionally verified daily.

Stool sampling

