	Astrovirus	ND	1-10 days (20)
Fungi	Enterocytozoon	18-38 days (21)	9-40 days (22)

Informed consent

All respondents will be consented in the Rohingya language and given a demographic and behaviour survey at the first time point. All questionnaires and surveys will be translated into Rohingya and back translated into English, with all data collection will be completed by Rohingya research assistants.

Data analysis

Data will be analysed using Stata version 15. The following analyses will be conducted

- Incidence rate ratios and associated 95% confidence intervals comparing diarrhoea and dysentery incidence between:
 - o Enhanced and basic surveys
 - o Survey method and stool analysis method
- Positive predictive value and associated 95% confidence interval of reported diarrhoea for the presence of enteric pathogens
- The association between diarrhoea presence and other potential markers of enteric infection such as MUAC and water-related diseases, measured for example by Jaccard's index
- A logistic regression of diarrhoea prevalence on demographic and health variables to examine association.

All missing data will be reported and assumed to be missing at random. The sample sizes proposed here would give us power to estimate the self-reported diarrhoea rate in each arm to a 95% confidence interval of approximately ±4 percentage points, assuming a point prevalence of 10%. We would also be able to estimate the positive and negative predictive values to approximately ±7 percentage points assuming values of 90%.

Data Management

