
Has this child had 3 or more loose or watery stools any day in the past 2 weeks?	Yes	No
Has this child had blood in their stool in the past 2 weeks?	Yes	No

If yes to either, did you seek treatment for either of these?	Yes	No	
	lf yes, where?		

Enhanced Survey (50% of respondants)

IDENTIFY OLDEST CHILD UNDER 5												
Mid-Upper Arm Circumference			cm									
*SHOW AMSTERDAM	Consistency	А	В	С	D			_				
CHART*Has the child had any of these stools in the past 2 weeks	Colour	1	2	3	4	5	6					
How long ago?	1		2			3		4	5	6	7	Other:
How many times on the worst day?	1		2			3		4	5	6	7	Other:
How many days did it last?	1		2			3		4	5	6	7	Other:

References

- 1. Vonberg, Ralf P., et al. "Duration of Fecal Shedding of Shiga Toxin–Producing Escherichia Coli O104:H4 in Patients Infected During the 2011 Outbreak in Germany: A Multicenter Study." *Clinical Infectious Diseases*, vol. 56, no. 8, 2013, pp. 1132–1140., doi:10.1093/cid/cis1218.
- 2. ECDC. Systematic Review on the Incubation and Infectiousness/Shedding Period of Communicable Diseases in Children. 2016, Systematic Review on the Incubation and Infectiousness/Shedding Period of Communicable Diseases in Children, ecdc.europa.eu/sites/portal/files/media/en/publications/Publications/systematic-review-incubation-period-shedding-children.pdf.
- 3. Murase, T, et al. "Fecal Excretion of Salmonella Enterica Serovar Typhimurium Following a Food-Borne Outbreak." *JOURNAL OF CLINICAL MICROBIOLOGY*, vol. 38, no. 9, 2000.
- 4. Gunn, John S., et al. "Salmonella Chronic Carriage: Epidemiology, Diagnosis, and Gallbladder Persistence." *Trends in Microbiology*, vol. 22, no. 11, 2014, pp. 648–655., doi:10.1016/j.tim.2014.06.007.
- 5. Janssen, R., et al. "Host-Pathogen Interactions in Campylobacter Infections: the Host Perspective." *Clinical Microbiology Reviews*, vol. 21, no. 3, 2008, pp. 505–518., doi:10.1128/cmr.00055-07.
- 6. South Australia Health. "Shigella Infection Including Symptoms, Treatment and Prevention." SA Health, 2018, www.sahealth.sa.gov.au/wps/wcm/connect/public+content/sa+health+internet/health+topics/health+conditions+prevention+and+treatment/infe ctious+diseases/shigella+infection/shigella+infection+-+including+symptoms+treatment+and+prevention.
- 7. Weil, Ana A., et al. "Bacterial Shedding in Household Contacts of Cholera Patients in Dhaka, Bangladesh." *The American Journal of Tropical Medicine and Hygiene*, vol. 91, no. 4, 2014, pp. 738–742., doi:10.4269/ajtmh.14-0095.

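### The planned logistic regression has no term for the randomised survey arm, so it averages associations over two different questionnaires and cannot show whether an association depends on the questionnaire.

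*Protocol*

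**What the plan says.** The last analysis listed in the protocol's Data analysis section is "A logistic regression of diarrhoea prevalence on demographic and health variables to examine association". It names two classes of predictor. Survey arm belongs to neither, and no arm term, interaction or per-arm fit is mentioned.

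The outcome depends on arm. Under Diarrhoea survey, "Households will be randomised in a 1:1 ratio into the basic survey" or the enhanced one. In Appendix 3 the basic form asks one yes/no question on stool frequency, "Has this child had 3 or more loose or watery stools any day in the past 2 weeks", plus one on blood in the stool. The enhanced form shows a stool chart, graded by consistency and colour, and asks "CHART*Has the child had any of these stools in the past 2 weeks" (the first word belongs to the form's instruction). It then asks how long ago, how many times on the worst day and for how many days. The protocol gives no rule that turns these answers into the basic form's yes or no.

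A sub-aim under Aims and Objectives is "To assess the relative differences between" the standard and enhanced questionnaires. The analysis listed for it is an incidence rate ratio with a 95% confidence interval for "Enhanced and basic surveys".

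**The concern.** The regression's outcome is one variable in name but two in measurement: half the households supply it through one instrument and half through another. The Background says that people may judge loose stools differently and that a pictorial survey may reduce such biases. If so, a respondent characteristic such as education could be related to reporting under one questionnaire and not under the other. A single model without arm reports one odds ratio for both. A reader could take it as describing diarrhoea when part of it describes the questionnaire.

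The planned rate ratio shows whether one questionnaire yields more reports overall. It does not show whether the extra or missing reports come from particular kinds of respondent. Arm is known for every household and education is asked of all of them, so the information is already collected. What is at stake is the reading of a secondary, descriptive analysis. The primary predictive values are not touched.

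**Working it through.** **Inputs from the protocol.** "400 households will be recruited through random household sampling" (Sampling), allocated 1:1, so 400 / 2 = 200 per arm. The Data analysis section says the sample would allow the study to "estimate the self-reported diarrhoea rate in each arm to a 95% confidence interval of approximately ±4 percentage points, assuming a point prevalence of 10" per cent.

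**The protocol's own figure.** Half-width = 1.96 × √(p(1 − p)/n). With p = 0.10 and n = 200 this is 1.96 × √(0.09/200) = 0.0416, or 4.2 points. The stated ±4 reproduces, which confirms about 200 per arm. The protocol gives no figure for the regression.

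**Assumptions for the rest.** A binary covariate is present in half the households and independent of arm. The basic-arm rate is 10%. Enhanced-arm rates and all odds ratios are assumed, because the protocol gives none.

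**1. Averaging.** Let the covariate have odds ratio 0.5 under the basic questions and 1.0 under the enhanced ones.

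| | Covariate absent | Covariate present | Odds ratio |
|---|---|---|---|
| Basic | 10.0% | 5.3% | 0.5 |
| Enhanced | 20.0% | 20.0% | 1.0 |
| Pooled | 15.0% | 12.6% | 0.82 |

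Basic: odds 0.1111 × 0.5 = 0.0556, a proportion of 5.3%. Pooled: (0.1263/0.8737) / (0.15/0.85) = 0.1446/0.1765 = 0.82. Other assumed pairs behave alike for enhanced rates of 10% to 20%: odds ratios of 1 and 2 pool to 1.40 to 1.54, and 1 and 3 to 1.68 to 1.95.

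**2. Does an arm main effect repair this?** The Mantel-Haenszel odds ratio stratified by arm is Σ(ad)/Σ(bc) for equal strata:
(0.0526 × 0.90 + 0.20 × 0.80) / (0.9474 × 0.10 + 0.80 × 0.20) = 0.2074/0.2547 = 0.81.
That is against 0.82 without arm, so adjustment still gives one number for two different associations.

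**3. Dilution from omitting arm.** Here the odds ratio is 2 in both arms.

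| Enhanced rate | Odds ratio without arm | Loss on log scale |
|---|---|---|
| 10% | 2.00 | 0% |
| 15% | 1.99 | under 1% |
| 20% | 1.97 | 2% |
| 30% | 1.91 | 6% |
| 40% | 1.84 | 12% |

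The loss is 1 − ln(odds ratio without arm)/ln 2; at 20% it is 1 − 0.680/0.693 = 0.02. At 10% and 20%, power to detect the odds ratio of 2 with 400 households is 65% without arm and 66% with it.

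**4. What by-arm estimates can deliver.** Take odds ratio 1 in the basic arm (10% and 10%) and 2 in the enhanced arm (14.6% and 25.4%, averaging 20%), with 100 households per cell. The variance of the log ratio of odds ratios is Σ[1/(100p) + 1/(100(1 − p))] over the four cells:
- basic arm: 2 × (1/10 + 1/90) = 0.222
- enhanced arm: 0.080 + 0.053 = 0.133
- total 0.355, standard error 0.596

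Power = Φ(0.693/0.596 − 1.96) = Φ(−0.80) = 21%. Across the assumed settings with a two-fold ratio the range is 16% to 21% in one round, and 28% to 38% if the two rounds are treated as independent. For a three-fold ratio it is 34% to 44% and 60% to 73%. The basic-arm odds ratio alone has standard error √0.222 = 0.471, so an estimate of 1.0 carries a 95% interval of about 0.40 to 2.52.

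**The case against.** The strongest reply is that this reads much into one line. The protocol does not say that the arms are pooled, that arm is excluded or that its predictor list is complete. Exact covariates for a secondary model are often left to a statistical analysis plan, which may exist. This stands in part: pooling is the natural reading, not a stated fact. But the protocol does fix the classes of predictor, and the study's one randomised factor is outside them. Elsewhere in the same section it names the arms when it wants them compared.

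A second reply is that the questionnaire comparison is already covered by the rate ratio, and that no aim asks whether method modifies covariate associations. That is right as far as overall rates go, so a reader who infers that the protocol discards the arm contrast goes too far. Only the association by method is missing.

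Three stronger readings are tempting and are not supported:
- A reader might infer that omitting arm biases or dilutes the odds ratios. Arm is randomised, so it does not confound. The shrinkage reflects the difference between a marginal and a conditional odds ratio, and it is negligible unless reporting rates differ greatly. The protocol's only rate is 10%, applied to each arm, at which there is none.
- A reader might infer a material loss of power. At assumed rates of 10% and 20% it is about one percentage point.
- A reader might link this to the differential reporting mentioned in the Executive Summary. That text concerns being observed or receiving an intervention, not the type of questionnaire.

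**Conclusion.** The point holds in a limited form. As written, the regression mixes two measures of reported diarrhoea and has no term to show whether an association depends on which was used, although comparing them is a sub-aim. The consequence is averaging: a pooled odds ratio lies between the two arm-specific ones and may describe neither, as with 0.82 from 0.5 and 1.0. How much this matters depends on whether associations really differ by method, which the documents do not say. The example about education is an illustration, not a prediction.

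The conclusion rests on reading the line as one model over all households, and on assumed enhanced-arm rates and odds ratios. It does not rest on attenuation, power or confounding. The severity is low: a worthwhile, inexpensive improvement to a descriptive secondary analysis that leaves the primary outcomes unaffected.

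**What to change.** In the Data analysis section, state that the logistic regression includes survey arm, and survey round wherever both rounds enter one model. For a few respondent variables named in advance, such as education, report odds ratios with 95% confidence intervals separately by arm, or the arm-by-variable interaction, and label these exploratory. The arm main effect alone does not answer the question. The by-arm odds ratios or the interaction are the part that does. State also which enhanced-form answers count as reported diarrhoea in this model. Choose variables recorded in both arms: the sample survey lists mid-upper arm circumference only on the enhanced form, so it cannot support this comparison.

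The cost is a sentence or two and a few model terms, with no new data. The drawback is imprecision: with about 200 households per arm, interaction power is roughly 16% to 21% for a two-fold ratio of odds ratios in one round, under the assumed rates. Report estimates and intervals, and do not read a non-significant interaction as evidence that the questionnaires agree.

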Appendix 3: Sample Survey

Data Collection	Log Book (Sepa	arated Data					
Name							
Phone Number							
Household Barcode	e SCAN BARC	ODE					
Survey Data (Se	parate from Lo	g Book)					
RA	1	2	3	4			
EA	_	_	_	_			
Date							
Household	SCAN		•	•			
Barcode	BARCODE						

Resident Information (all respondents)

Name	Age	Sex	Education Level	Occupation	Health Conditions	Time Spent in Bangladesh	Relationship to Respondent
RESPONDANT							
SPOUSE IF PRESENT							
Child/Other Family							
Child/Other Family							
Child/Other Family							

Child/Other Family				
Child/Other Family				
Child/Other Family				

Household Information (all respondents)

What is the main source of drinking water for your household?	Piped water into home	Piped water into plot	Piped water to tap	Borehole	Dug well	Spring	Rain	Truck	Cart	Surface Water	Bottled Water
Where is that water source located	In my home	In my plot	In a public space								
How long does it take you to get there?		Minutes									
Do you share this with other households?	Yes	No									
	If yes, how many		Households								
	If yes, how long do you have to wait for water										
			Minutes								

Do you do anything to make this water safe to drink?	Yes	No									
	If yes, what?	Boil	Bleach/Chlorine	Cloth Strain	Filter	Solar disinfection	Sit and Settle	Other:			
Can I see where you use the toilet?	Yes	No									
	lf yes, describe:	Flush toilet to sewer	Pit Latrine	VIP Latrine	Flush toilet to Latrine	Composting Toilet	Bucket Toilet	Open Defecation	Other:		
How many people use this toilet		People									
Is this toilet separated by sex	Yes	No									
Do you feel safe using this toilet during the day?	Yes	No									
Do you feel safe using this toilet when dark?	Yes	No								_	
How do you wash your hands?	Water alone	Water with Soap	Alcohol Based Sanitizer	Non- Alcohol Based Sanitizer	Does not wash hands	Other:					
When do you wash your hands? (all that apply)	After Defecation	After cleaning a child's stool	Before Feeding a Child	Before Eating	Before preparing food	Other:					

Do you own livestock?	Yes		No							
Where do you normally seek healthcare?										
OBSERVE MATERIAL OF FLOOR	Natural Floor	Wood	Bamboo	Tarp	Finished Floor	Other:				
OBSERVE MATERIAL OF ROOF	No roof	Thatch	Bamboo	Wood	Cardboard	Tin	Ceramic	Cement	Tent	Other:
OBSERVE WATER STORAGE VESSEL	Open Bucket	Closed bucket	Bottle	Jerry Can	Bucket	Other:				

Basic Survey (50% of respondants)

IDENTIFY OLDEST CHILD UNDER 5

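### The ±4 and ±7 point precision figures assume independent households, while sampling works outward from central points and no design effect is stated

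*Protocol*

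**What the plan says.** The Sampling section of the Protocol describes a "two arm RCT design in which 400 households will be recruited through random household sampling", covering formal and informal camps. Under its EPI method, a "series of random angles and distances from a pre-determined central point (e.g. a water tap) will be generated", and the household nearest each mapped location is taken. The section does not say how many central points there will be or how many households each will yield.

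Under Diarrhoea survey, "Households will be randomised in a 1:1 ratio into the basic survey" or the enhanced one, so the household is the unit of randomisation.

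The Data analysis section gives the precision: "power to estimate the self-reported diarrhoea rate in each arm to a 95% confidence interval of approximately ±4 percentage points" at an assumed prevalence of 10%, and about ±7 points for positive and negative predictive values of 90%. No ICC or design effect appears. The same section lists predictive values with 95% intervals and "A logistic regression of diarrhoea prevalence on demographic and health variables to examine association". It names Stata 15 but no variance estimator.

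The household form in Appendix 3 asks of the water source, "Do you share this with other households", and how many people use the toilet. It also has an undefined field, EA, beside the research assistant code.

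**The concern.** A series of draws around one water tap tends to give households that live near one another and may share water and latrines. Enteric infection and reported diarrhoea are plausibly more alike among such households than across the camps as a whole. If so, 200 households per arm carry less information about prevalence than 200 independent ones, and the same applies to the stool samples behind the predictive values.

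At stake is whether the stated precision describes the design or only its best case. The predictive values are the primary outcomes according to the Executive Summary, and the prevalence half-width is the other quantity used to justify the sample size.

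**Working it through.** **Inputs from the Protocol.** 400 households allocated 1:1, so 200 per arm. One child per household (the oldest under 5), so there is no clustering within households. Prevalence 10%, predictive value 90%. Stool samples from 20 households reporting and 20 not reporting diarrhoea, per arm and time point, so each predictive value pooled over arms and rounds rests on 20 × 2 × 2 = 80 stools.

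**Reproducing the stated figures** with half-width = 1.96 × √(p(1−p)/n):

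- Prevalence: 1.96 × √(0.1 × 0.9/200) = ±4.16 points, stated as about ±4.
- Predictive value: 1.96 × √(0.9 × 0.1/80) = ±6.57 points, stated as about ±7.

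Both match with a design effect of 1.

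**Allowing for clustering.** Design effect (DEFF) = 1 + (m − 1) × ICC, where m is the number of observations per central point, and the half-width is multiplied by √DEFF. For prevalence m = 200/points; for a predictive value m = 80/points. ICC and number of points are assumptions, as is an even spread over points. At ICC 0.05:

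| Central points | Prevalence: m, DEFF | Half-width | Predictive value: m, DEFF | Half-width |
|---|---|---|---|---|
| 40 | 5, 1.20 | ±4.55 | 2, 1.05 | ±6.74 |
| 20 | 10, 1.45 | ±5.01 | 4, 1.15 | ±7.05 |
| 10 | 20, 1.95 | ±5.81 | 8, 1.35 | ±7.64 |

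With 20 points, ICC 0.02 gives DEFF 1.18 and ±4.52 for prevalence; ICC 0.10 gives 1.90 and ±5.73. With one household per arm per point the DEFF is 1 and ±4.16 stands.

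**How much clustering the rounded figures tolerate.**

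- ±4 remains correct to the nearest point while the half-width is below 4.5, that is up to DEFF = (4.5/4.158)² = 1.17. At ICC 0.05 this means m ≤ 1 + 0.171/0.05 = 4.4, or at least 46 central points. At ICC 0.02 it means m ≤ 9.6, or at least 21.
- ±7 remains correct up to DEFF = (7.5/6.574)² = 1.30. At ICC 0.05 this means m ≤ 7.0, or at least 12 points.

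**The between-arm contrast.** With households randomised within points, the shared point effect cancels in the difference, and its DEFF is about 1 − ICC = 0.95. A beta-binomial simulation (10% prevalence, ICC 0.05, arms balanced within points) agreed. With 20 and 10 points, the DEFF for one arm's prevalence was 1.46 and 1.93; for the arm difference it was 0.96 and 0.95.

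**The case against.** The strongest reply is that the Protocol never says households are taken in groups. Each mapped location has its own random angle and distance, and the central point is mentioned in the singular without a count or a take. With many points and few households at each, the design effect is close to 1 and the stated figures hold. This is right, and it makes the point conditional. It does not remove it: the text refers to a series of draws from a point, and ±4 needs roughly 46 points at ICC 0.05, a number the Protocol does not supply.

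Second, a reader might infer that the planned confidence intervals ignore clustering and so will cover less than 95%. The Protocol does not support this. It lists the quantities to be estimated, not the standard errors, and any of them can be computed with cluster-robust variance. That choice may properly sit in a statistical analysis plan that is not at hand. The precision statement is different, because it stands in the Protocol and its arithmetic fixes the design effect at 1.

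Third, a reader might infer that the logistic regression will produce false associations. That would need covariates that are nearly constant within a point and an analysis that ignores the point. The Protocol speaks of demographic and health variables, the form records water and toilet items household by household, and the variance method is open. No error rate can be attached to the plan as written.

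Finally, the primary-outcome figure is fairly robust: with 20 points at ICC 0.05 it is still about ±7. This stands, subject to stools being spread evenly over points. Stools come from the first eligible households in each arm, and the visiting order is not stated, so they could be more concentrated than the survey sample.

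**Conclusion.** The point holds in a limited, conditional form. The stated ±4 and ±7 are best-case figures that assume independent households, and the Protocol gives neither the number of points nor the correlation needed to show that the sampling method delivers them.

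If several households come from each point and diarrhoea is correlated within points, single-arm prevalence is the estimate most affected: between ±4.55 and ±5.81 for 40 down to 10 points at an assumed ICC of 0.05. Predictive values are affected less, at ±7.05 to ±7.64 for 20 down to 10 points. These are illustrations over assumed values, not estimates of the trial's true precision. The randomised comparison of the two questionnaires is essentially untouched and should not be cited as weakened.

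**What to change.** - **Sampling section:** state the planned number of central points and the households to be taken per point, and confirm that the sampling point is recorded for every household. If EA on the form means the sampling area, define it and use it; if not, add a field before fieldwork starts.
- **Data analysis section:** restate both half-widths as a range with the assumed design effect shown. As a template to be filled with the sponsor's own assumptions: about ±4.2 to ±5.8 points for prevalence per arm (design effect 1 to 1.95) and about ±6.6 to ±7.6 points for predictive values (design effect 1 to 1.35).
- **Analysis:** specify standard errors clustered on sampling point for single-arm prevalence, positive and negative predictive values and the logistic regression, with a small-sample correction if points are few. If a statistical analysis plan already says this, a cross-reference is enough.

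The cost is a few sentences, one recorded variable and a standard Stata option, with no additional households or stools. The downside is somewhat wider intervals and less favourable stated precision.
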